1. STUDY OBJECTIVES

1.1 Primary Objective

To evaluate the safety and tolerability of VIS649 in healthy subjects

1.2 Secondary Objectives

- To characterize the pharmacokinetic (PK) profile of VIS649
- To evaluate the effect of ethnicity on the PK profile of a single intravenously (IV) administered dose of VIS649 in healthy Japanese and non-Japanese subjects
- To characterize the levels of anti-drug antibodies
- To characterize the effect of VIS649 on pharmacodynamic (PD) parameters including:
 - changes in serum total IgA, IgG and IgM concentrations and time to recovery.
 - changes in circulating lymphocyte populations in cohorts 1-4 only (this assessment will be done for all lymphocytes, and also for lymphocyte subsets that are noted to show changes from baseline)

PAREXEL International
Statistical Analysis Plan

- To assess ADA status impact on VIS649 PK parameters

■ [REDACTED]

2. ENDPOINTS

2.1 Primary Endpoint

- Safety Endpoint
 - The proportion of subjects with AEs and serious adverse events (SAEs) following administration of VIS649; safety will be assessed from the time of study drug administration to the end-of-study participation.
 - The following safety variables will be collected and recorded at regular intervals during the study:
 - Adverse event assessments
 - Clinical laboratory tests (hematology, clinical chemistry and urinalysis)
 - Vital signs (sitting BP, heart rate, temperature and respiratory rate [RR])
 - Twelve-lead ECG
 - Adjunctive procedures
 - Physical examination

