1. The first two subjects of each cohort will be discharged 24 hours (Day 2) after the study infusion. All other subjects are discharged on Day 2, 24 hours after study infusion. Discharge from the Phase 1 unit will not occur prior to performing the 24 h post infusion study procedures.

Visterra Inc.
VIS649-101

Final 1.0
3/Jun/2019

TP-EP.BS-WW-001-05
Effective date: 29 Jul 15
Related to: SOP-EP.BS-WW-002

PAREXEL International
Statistical Analysis Plan

2. Optional Visit at Week 20 is only to be made if immunoglobulin levels (IgG, IgM, or IgA) have not returned to normal range by Week 16; the Optional Visit at Week 24 is only to be made if immunoglobulin levels have not returned to normal range by Week 20. If immunoglobulin levels (IgG, IgM, or IgA) have not returned to normal range by Week 16 for one or more subjects, the entire cohort will complete Week 20 and Week 24.
3. Vitals signs at Screening and Day -1 will include height and weight, to permit estimated creatinine clearance calculation, as well as blood pressure (bp), heart rate (hr), respiratory rate (rr) and temperature. Subject weight will be measured after admission to the research unit (Day -1) and will be used by pharmacy staff for subject-specific dose calculation. Vital signs at other timepoints will be limited to temperature (Day -1 and Day 1 pre-dose only), bp, hr, and rr. Vital signs measurements on Day 1 will be recorded within 30 minutes prior to the start of the infusion, then every 15 minutes until the infusion is complete and post infusion at 60 minutes, 2 hours and 4 hours. On subsequent visits, vital signs will be recorded, as possible, at approximately the same time of day, if convenient. Post-dose bp should be based on the end of infusion time.
4. On Day 1 electrocardiograms will be done within 30 minutes prior to infusion and at the end of the infusion (+10 min).
5. On the day of study infusion (Day 1), blood samples for PK analysis will be collected prior to start of the infusion, at the end of infusion (60 minutes), and at 2 hours, 8 hours, and 24 hours post end of infusion. All subjects will have PK samples drawn on Days 3, 7, and Weeks 2 (Day 14), 4 (Day 28), 6 (Day 42), 8 (Day 56), 10 (Day 70), and 16 (112).

■ [REDACTED]
■ [REDACTED]
■ [REDACTED]

7. This sampling will not be done for cohort 5.
9. This sampling will be pre-vaccination in cohort 5.

PAREXEL International Statistical Analysis Plan

Cohorts are planned as follows:

Table 2 Cohorts and Dose Administration

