4.3 Statistical Analysis Methods

4.3.1 Listings and Descriptive Statistics

All original and derived parameters will be listed. Listings will be by cohort, dose, subject and, where applicable, time post dose.

All listings will include repeated and unscheduled measurements.

The following rules will apply to any repeated measurements:

- If the repeated measurement occurs prior to the first dose of study drug, then the last obtained value of any repeated measurement will be used in the descriptive statistics.
- If the repeated measurement occurs after the first dose of study drug, then the original value of any repeated measurements will be used in the descriptive statistics.

Frequency counts (number of subjects [n] and percentages) will be presented for each qualitative variable. Descriptive statistics (n, mean, standard deviation [SD], median, minimum and maximum) will be calculated and presented for each quantitative variable (unless otherwise stated).

PAREXEL International Statistical Analysis Plan

The rules with regards to the presentation of the frequency counts (number of subjects [n] and percentages) are as follows: if frequency count is 0, percentage will not be presented; if percentage is 100%, no decimal places will be given.

All descriptive statistics will be presented by treatment (dose). Subjects who receives placebo within cohort 1 - 4 will be presented as pooled placebo group, and subjects receiving placebo within cohort 5 will be used as individual placebo group as well. Data grouped from cohort 1-4, cohort 5 only and overall (all cohorts) may be analysed separately. In addition, a pooled VIS649 group (i.e. all subjects who receive VIS649 regardless of dose) will be presented for demographics, disposition, and adverse event. The baseline for all measurements (where applicable) will be the last pre-dose measurement unless specified.

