4.3.6.2 Subject Disposition

The completion status and the reason for discontinuation of subjects using the randomized population will be listed [Listing 16.2.1.1] and summarized [Table 14.1.1]. The number and percentage of subjects entering and completing each treatment of the clinical study will be presented, including the number and percentage of subjects dosed, the frequency and percentage of subjects completing the treatment, and the frequency and percentage of subjects completing the study,, subjects withdrawing early, and primary reason for withdrawal will be included the summary table.

Listing of the informed consent will be presented using the randomized population [Listing 16.2.1.2].

Subjects who did not meet the inclusion criteria will be listed [Listing 16.2.1.3], and subjects who did meet the exclusion criteria will be listed [Listing 16.2.1.4].

Subject visits information will be listed using the safety population [Listing 16.2.1.5].

PAREXEL International Statistical Analysis Plan

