4.3.11.1 Adverse Events

The following listing and tables will be produced:

- All Pre-treatment and treatment-emergent AE [Listing 16.2.7].
- All Serious AEs (if applicable) [Listing 14.3.2.1].
- All Adverse Events Leading to Discontinuation (if applicable) [Listing 14.3.2.2].

The following information will be included in the listings: Verbatim, system organ class (SOC), preferred term (PT), AE onset date (and time) and study day, AE end date (and time) and duration (days), severity, relationship to IMP, AE outcome, TEAE indicator flag and SAE indicator flag.

An overall summary of all treatment-emergent adverse events [Table 14.3.1.1] will present the number and percentage of subjects, as well as number of events, according to the following categories:

- All treatment emergent adverse events
- Emergent adverse events Related to IMP

PAREXEL International Statistical Analysis Plan

- Mild treatment emergent adverse events
- Moderate treatment emergent adverse events
- Severe treatment emergent adverse events
- Serious treatment emergent adverse events
- Treatment emergent adverse events leading to early termination
- Deaths

Other summary tables for adverse events will include:

- Table 14.3.1.2: Number and Percentage of Subjects with Treatment Emergent Adverse Events by System Organ Class, and Preferred Term
- Table 14.3.1.3: Number and Percentage of Subjects with Treatment Emergent Adverse Events by System Organ Class, Preferred Term, and Severity
- Table 14.3.1.4: Number and Percentage of Subjects with Treatment Emergent Adverse Events “Related to IMP” by System Organ Class, Preferred Term, and Severity
- Table 14.3.1.5: Number and Percentage of Subjects with Treatment Emergent Adverse Events “Not Related to IMP” by System Organ Class, Preferred Term, and Severity

If a subject has multiple AEs with the same preferred term but occurring after each dose administration, then one AE will be counted for each treatment.

Adverse event summaries will be ordered in terms of decreasing frequency for SOC, and PT within SOC, and then alphabetically for SOC, and PT within SOC.

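### Minor and conditional: AE tables have no common time window, so extending only some of cohorts 1-4 past Week 16 gives dose columns and pooled placebo unequal follow-up

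*SAP*

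**What the plan says.** - **Window.** SAP 2.1 makes the proportion of subjects with AEs and SAEs the primary endpoint and states that "safety will be assessed from the time of study drug administration to the end-of-study participation". SAP 4.1.4.1 collects AEs until the End-of-study Visit. It defines a TEAE by onset or worsening after dosing, with no last day.
- **Who attends Weeks 20 and 24.** SAP Table 1 footnote 2 (section 3.1) first says that "the Optional Visit at Week 24 is only to be made if immunoglobulin levels have not returned to normal range by Week 20". It then adds a rule at cohort level, for immunoglobulins: "not returned to normal range by Week 16 for one or more subjects, the entire cohort will complete Week 20 and Week 24".
- **Columns.** SAP 4.3.1 presents results by dose, and "Subjects who receives placebo within cohort 1 - 4 will be presented as pooled placebo group". Cohort 5 has its own placebo column.
- **Measure.** Under SAP 4.3.11.1 the overall AE table "will present the number and percentage of subjects, as well as number of events". The other AE tables also give numbers and percentages of subjects. No AE table gives follow-up time or limits events to a common period.
- **What is already listed.** AE listings carry "AE onset date (and time) and study day", and under SAP 4.3.6.2 "Subject visits information will be listed using the safety population".

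**The concern.** The two sentences of footnote 2 cannot both govern. By the first, attendance at Week 24 depends on the Week 20 result. By the second, a single unrecovered subject at Week 16 commits the whole cohort to both visits. Follow-up length, and with it the AE window, depends on which one applies.

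Under the whole-cohort sentence, active and placebo subjects in the same cohort keep equal planned follow-up. The AE tables, however, set each dose column beside the other dose columns and beside placebo pooled over four cohorts. If only some of those cohorts are extended, the columns cover different lengths of time. The trigger is immunoglobulin level, which the drug is designed to lower, so follow-up length could run with dose. A reader could then see a step in AE incidence between doses that comes only from longer observation.

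**Working it through.** **Durations.** The supplied protocol's synopsis gives about 20 weeks of participation, extendable to 28, including up to 4 weeks of screening. 4 + 16 = 20 and 4 + 24 = 28, so both figures reproduce. Post-dose follow-up is 16 or up to 24 weeks, a ratio of 24/16 = 1.5.

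**Inputs from the documents.** Cohorts 1-4 each have 7 active and 2 placebo subjects (SAP Table 2), so pooled placebo is 4 × 2 = 8.

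**Inputs assumed.** No drug effect on AEs; 16-week AE incidence p16 = 30%, 50% or 70%; hazard in Weeks 16-24 equal to a fraction f of the earlier hazard. The documents give none of these.

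**Pooled placebo follow-up, k of cohorts 1-4 extended to Week 24.** Mean = (8 × 16 + 2k × 8)/8 = 16 + 2k weeks: 18, 20 or 22 for k = 1, 2, 3, and 16 or 24 for k = 0 or 4.

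**Extended minus non-extended dose column.** pE = 1 − (1 − p16)^(1 + 0.5f); the difference is pE − p16.

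| f | p16 = 30% | 50% | 70% |
|---|---|---|---|
| 1 (constant hazard) | 11.4 points | 14.6 | 13.6 |
| 0.5 | 6.0 | 8.0 | 7.8 |
| 0.25 | 3.1 | 4.1 | 4.2 |
| 0 | 0 | 0 | 0 |

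Example: 1 − 0.5^1.5 = 64.6%, and 64.6 − 50 = 14.6 points. In a column of 7, the constant-hazard row is 0.80, 1.03 and 0.95 of a subject. The f = 0.5 row also describes an extended cohort that stops at Week 20 with constant hazard, since 20/16 = 1.25 = 1 + 0.5 × 0.5.

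**Extended column minus pooled placebo.** Placebo incidence is ((4 − k) × p16 + k × pE)/4, so the difference is (4 − k)/4 × (pE − p16).

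| k | f = 1 (30/50/70%) | f = 0.25 (30/50/70%) |
|---|---|---|
| 1 | 8.6 / 11.0 / 10.2 | 2.3 / 3.1 / 3.1 |
| 2 | 5.7 / 7.3 / 6.8 | 1.5 / 2.1 / 2.1 |
| 3 | 2.9 / 3.7 / 3.4 | 0.8 / 1.0 / 1.0 |

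A non-extended column falls short of pooled placebo by k/4 × (pE − p16), which is the same set of values with k = 1 and k = 3 exchanged.

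**Sampling error for scale.** One subject in 7 is 14 points. For 7 versus 8 at 50%, SE = √(0.25 × (1/7 + 1/8)) = 0.259, about 26 points.

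**With one common window.** Counting onset through day 112 gives every column 16 planned weeks, and the artefact is 0.

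**The case against.** **Hypothetical and small.** The problem needs one, two or three of cohorts 1-4 to be extended. The documents give no probability of that, and the immunoglobulin inclusion thresholds and predicted nadirs are redacted. After a single dose, AEs probably cluster early, which favours the lower rows of the table. All of this stands and is why the point is minor.

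**Already recoverable.** Onset study day and visits are listed, and SAP 4.3.5 has each cohort cleaned and soft-locked after Week 16. A day-112 count can therefore be made by hand. That also stands. A prespecified table would avoid a cut-off chosen after the data are seen, and the interim summaries stay blinded.

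**Full-period counting is legitimate.** It is, and it should remain primary so that late events, infections in particular, are not lost.

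**Version.** The end-of-study definition (protocol 7.4) comes from the supplied protocol, with up to 45 subjects. The SAP rests on Amendment 2 and plans 51. The SAP's own footnote 7 text on additional visits cannot be read. The SAP's open-ended window and footnote 2 do not depend on the protocol text.

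A reader might infer more, in three ways that the documents do not support:

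- **That active subjects are followed longer than placebo within a cohort.** This requires setting aside the whole-cohort sentence, under which they are followed alike.
- **That the all-dose VIS649 column is distorted against cohort 1-4 placebo.** The SAP plans "a pooled VIS649 group (i.e. all subjects who receive VIS649 regardless of dose) will be presented for demographics, disposition, and adverse event", but no sentence pairs that column with cohort 1-4 placebo alone. Cohort 5 also received a vaccine, so such a comparison would already be confounded.
- **That the higher doses will probably be extended.** Protocol 1.3 expects IgA below baseline for weeks in the higher dose cohorts. The trigger is the normal range at Week 16, not baseline, and the same section expects the single-dose effect on IgA to be transient.

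**Conclusion.** The point holds as minor and conditional. Footnote 2 contradicts itself whatever happens in the trial. If its whole-cohort sentence governs and cohorts 1-4 are only partly extended, the AE tables compare columns with unequal planned follow-up and do not show it.

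On the assumed rates, the largest effect is about one subject in a column of 7 between dose columns. Against pooled placebo it is at most 11.0 points (one cohort extended, constant hazard, 50%). It vanishes if none or all four cohorts are extended, or if no hazard remains after Week 16. Under the whole-cohort sentence it does not arise for cohort 5 against its own placebo.

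A reader might conclude that the primary safety result is biased. The documents do not support that: the AE comparison is descriptive, no AE test is planned, and sampling error exceeds the artefact. The risk is a misread table.

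**What to change.** 1. Reconcile the two sentences of SAP Table 1 footnote 2, so that planned follow-up per cohort is known.
2. In SAP 4.3.11.1, keep Tables 14.3.1.1-14.3.1.5 over the full period as primary.
3. Add supportive versions of Tables 14.3.1.1 and 14.3.1.2 limited to TEAEs with onset through study day 112, as a fixed day rather than the visit date.
4. Add a row giving the median and range of follow-up per column.

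A flag for onset after day 112 in Listing 16.2.7 is optional, because onset study day is already there. Events per subject-week would not be a good substitute. With a quarter of the earlier hazard after Week 16, an extended column's rate would be (16 + 8 × 0.25)/24 = 0.75 of a non-extended one with no drug effect.

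The cost is two tables and one row, from dates already collected. The endpoint, data collection and existing tables do not change. The downside is a second AE window to label; it must be marked supportive so that late infections are still read from the full-period tables. A small residue remains: with the ±3-day visit window, a subject last seen on day 109 has 3/112 = 2.7% less follow-up than the cut-off.

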2.2 Secondary Endpoints

- Characterization of anti-drug antibodies (ADA) levels

PAREXEL International

Statistical Analysis Plan

2.2.1 Pharmacokinetics Endpoints

The following PK parameters for VIS649 will be determined, as appropriate:

- C_{max} : Maximum serum VIS649 concentration determined directly from the concentration-time profile
- T_{max} : Time of maximum serum VIS649 concentration determined directly from the concentration-time profile
- AUC_{0-112d} : Area under the concentration-time curve from pre-dose (time 0) to the concentration on day 112
- AUC_{0-last} : Area under the concentration-time curve from pre-dose (time 0) to the last quantifiable concentration
- AUC_{0-inf} : Area under the concentration-time curve from pre-dose (time 0) extrapolated to infinite time [REDACTED]
- $t_{1/2}$: Terminal elimination half life
- V_d : Volume of distribution [REDACTED]
- CL : Clearance [REDACTED]

2.2.2 Pharmacodynamic Endpoints

- Changes in total serum IgG, IgA and IgM concentrations and time to recovery
- Changes in circulating lymphocyte populations in cohorts 1-4 only (this assessment will be done for all lymphocytes, and also for lymphocyte subsets that are noted to show changes from baseline).
-

Visterra Inc.
VIS649-101

Final 1.0
3/Jun/2019

TP-EP.BS-WW-001-05

Effective date: 29 Jul 15

Related to: SOP-EP-BS-WW-002

Page 15 of 68

PAREXEL International
Statistical Analysis Plan

3. STUDY DESIGN

3.1 Study Design

This is a phase 1, randomized, placebo-controlled, double-blind, and single ascending dose study to investigate the safety, tolerability, PK/PD of the IV administration of VIS649 in healthy subjects.

The study will be conducted in five sequential dosing cohorts. Cohorts 1-4 will enroll 9 subjects per cohort. Cohorts 1-4 will enroll 4 Japanese subjects and will be randomized to VIS649 or placebo in a ratio of 7:2 (7 active, 2 placebo). The fifth cohort will enroll up to 15 subjects with targeted but non-mandatory enrollment of up to 5 Japanese subjects. The subjects in cohort 5 will be randomized to VIS649 or placebo in a ratio of 10:5 (10 active, 5 placebo). In addition, all subjects in cohort 5 will receive TENIVAC® vaccine.

Sentinel subjects will be utilized in cohorts 1-4 (but not in cohort 5); the first two subjects in each cohort will be randomized to receive either VIS649 (n=1) or placebo (n=1) and will receive study drug at least 24 hours before the remaining subjects in the cohort (7 subjects) are dosed. These 2 subjects shall remain confined to the study center for 24 hours after study drug administration. Cohort 5 does not require sentinel subjects as the dose of VIS649 has already been evaluated in cohort 3.

The Schedule of Assessments is listed in Table 1.

PAREXEL International
Statistical Analysis Plan

Table 1 Schedule of Assessments

Activity	Screen	Base - line	Post-Dosing Period Assessments																Additional Visits ⁷	
			BL D-1	D1	D2	D3	W1/ D7	W2/D 14	W3/D 21	W4/D 28	D31 ⁹	W5/ D35	W6/ D42	W7/ D49 (cohorts 1-4 only)	W8/ D56	W10/ D70	W12/ D84	W14/ D98	W16/ D112	W 20
Time Point (Day)	Days - 28 to -1	BL D-1 pre-dose																		
+/- visit allowance	N/A	N/A	N/A	N/A	+1	+/-1	+/-3	+/-3	+/-3	+/-3	+/-1	+/-3	+/-3	+/-3	+/-3	+/-3	+/-3	+/-3	+/-5	+/-5
In-house Day		x	x	x1																
Ambulatory Visit	x				x	x	x	x	x	x	x	x	x	x	x	x	x	x ²	x ²	
Procedures																				
Informed Consent/HIPAA	x																			
Verify Inclusion/exclusion criteria	x	x																		
Demographics & Medical History	x																			
Pregnancy Test (Serum β-hCG)	x																		x	
Pregnancy Test (urine dip stick)		x																		
Serology - HBsAG, Hepatitis C, HIV-test	x																			
Drug & alcohol toxicology screen	x	x																		
Physical Examination - Full	x	x																		
Physical					x				x						x		x		x	

PAREXEL International
Statistical Analysis Plan

Activity	Screen	Base - line	Post-Dosing Period Assessments																	Additional Visits ⁷	
			Days - 28 to -1	BL D-1 pre-dose	D1	D2	D3	W1/ D7	W2/D 14	W3/D 21	W4/D 28	D31 ⁹	W5/ D35	W6/ D42	W7/ D49 (cohorts 1-4 only)	W8/ D56	W10/ D70	W12/ D84	W14/ D98	W16/ D112	W 20
Time Point (Day)																					
+/- visit allowance	N/A	N/A	N/A	N/A	+1	+/-1		+/-3	+/-3	+/-3	+/-3	+/-1	+/-3	+/-3	+/-3	+/-3	+/-3	+/-3	+/-3	+/-5	+/-5
Examination - Brief																					
Vital Signs ³	x	x	x		x	x	x		x		x				x		x		x		
ECG	x	x	x ⁴																		
Concomitant Medications	x	x	x		x	x	x	x	x	x	x	x	x	x	x	x	x	x	x	x	
AE Check		x	x	x	x	x	x	x	x	x	x	x	x	x	x	x	x	x	x	x	
IV Study Infusion			x																		
Laboratory Assessments																					
Serum Chemistry / Coagulation	x	x			x		x														
Urinalysis	x	x			x				x						x				x		
Hematology (CBC with differential)	x	x			x		x		x						x		x				
Blood Sampling for PK ⁵			x ⁵	x ⁵	x	x	x		x ¹⁰			x		x	x	x	x	x	x	x	
Blood Sampling for PD (Immunoglobulins)	x	x			x	x	x	x	x ¹⁰		x	x	x	x	x	x	x	x	x	x	
Blood Sampling for Ig subtypes		x				x			x ¹⁰			x		x	x	x	x	x	x	x	
Blood Sampling		x							x									x	x	x	

Visterra Inc.
 VIS649-101

Final 1.0
 3/Jun/2019

TP-EP.BS-WW-001-05
 Effective date: 29 Jul 15
 Related to: SOP-EP.BS-WW-002

PAREXEL International
Statistical Analysis Plan

Activity	Screen	Base - line	Post-Dosing Period Assessments																		Additional Visits ⁷	
			D1	D2	D3	W1/ D7	W2/D 14	W3/D 21	W4/D 28	D31 ⁹	W5/ D35	W6/ D42	W7/ D49 (cohorts 1-4 only)	W8/ D56	W10/ D70	W12/ D84	W14/ D98	W16/ D112	W 20	W24		
Time Point (Day)	Days - 28 to -1	BL D-1 pre-dose																				
+/- visit allowance	N/A	N/A	N/A	N/A	+1	+/-1	+/-3	+/-3	+/-3	+/-1	+/-3	+/-3	+/-3	+/-3	+/-3	+/-3	+/-3	+/-3	+/-3	+/-5	+/-5	
for PD (lymphocyte populations) ⁸																						

Blood sampling for ADA		x								x ¹⁰						x				x	x ⁷	x ⁷
Vaccine Administration ^{9, 10}										x												
Tetanus/diphtheria serology ^{9, 10}										x ¹⁰	x	x	x		x		x		x		x	

Abbreviations: ADA: Anti-drug Antibody; AE: Adverse event; D: Day; ECG: Electrocardiogram; HBsAG: Hepatitis B surface antigen; HIPAA: Health Insurance Portability and Accountability Act; HIV: Human Immunodeficiency Virus; Ig: Immunoglobulin; IV: Intravenous; N/A: Not Applicable, PD: Pharmacodynamics; PK: Pharmacokinetics; W: Week.

1. The first two subjects of each cohort will be discharged 24 hours (Day 2) after the study infusion. All other subjects are discharged on Day 2, 24 hours after study infusion. Discharge from the Phase 1 unit will not occur prior to performing the 24 h post infusion study procedures.

Visterra Inc.
VIS649-101

Final 1.0
3/Jun/2019

TP-EP.BS-WW-001-05
Effective date: 29 Jul 15
Related to: SOP-EP.BS-WW-002

PAREXEL International
Statistical Analysis Plan

2. Optional Visit at Week 20 is only to be made if immunoglobulin levels (IgG, IgM, or IgA) have not returned to normal range by Week 16; the Optional Visit at Week 24 is only to be made if immunoglobulin levels have not returned to normal range by Week 20. If immunoglobulin levels (IgG, IgM, or IgA) have not returned to normal range by Week 16 for one or more subjects, the entire cohort will complete Week 20 and Week 24.
3. Vitals signs at Screening and Day -1 will include height and weight, to permit estimated creatinine clearance calculation, as well as blood pressure (bp), heart rate (hr), respiratory rate (rr) and temperature. Subject weight will be measured after admission to the research unit (Day -1) and will be used by pharmacy staff for subject-specific dose calculation. Vital signs at other timepoints will be limited to temperature (Day -1 and Day 1 pre-dose only), bp, hr, and rr. Vital signs measurements on Day 1 will be recorded within 30 minutes prior to the start of the infusion, then every 15 minutes until the infusion is complete and post infusion at 60 minutes, 2 hours and 4 hours. On subsequent visits, vital signs will be recorded, as possible, at approximately the same time of day, if convenient. Post-dose bp should be based on the end of infusion time.
4. On Day 1 electrocardiograms will be done within 30 minutes prior to infusion and at the end of the infusion (+10 min).
5. On the day of study infusion (Day 1), blood samples for PK analysis will be collected prior to start of the infusion, at the end of infusion (60 minutes), and at 2 hours, 8 hours, and 24 hours post end of infusion. All subjects will have PK samples drawn on Days 3, 7, and Weeks 2 (Day 14), 4 (Day 28), 6 (Day 42), 8 (Day 56), 10 (Day 70), and 16 (112).

■ [REDACTED]
■ [REDACTED]
■ [REDACTED]

7. This sampling will not be done for cohort 5.
9. This sampling will be pre-vaccination in cohort 5.

PAREXEL International Statistical Analysis Plan

Cohorts are planned as follows:

Table 2 Cohorts and Dose Administration

Cohorts	Number of Subjects	Treatment
Cohort 1	N=7	VIS649 0.5 mg/kg
	N=2	Placebo
Cohort 2	N=7	VIS649 2.0 mg/kg
	N=2	Placebo
Cohort 3	N=7	VIS649 6.0 mg/kg
	N=2	Placebo
Cohort 4	N=7	VIS649 12 mg/kg
	N=2	Placebo
Cohort 5	N=10	VIS649 6.0 mg/kg plus vaccine
	N=5	Placebo plus vaccine

